Patients will initially be randomized into 1 of 3 treatment groups: 2 fixed dose levels of LY3202626 (3 mg and 12 mg per day) and placebo (1:1:1) until approximately 45 participants are enrolled in each arm; then randomization will change to 1:1 with subjects entering either the 12 mg or placebo arm. Treatment duration for all subjects will be 52 weeks.

Number of Patients:

Approximately 380 patients will be enrolled for approximately 320 completed evaluable patients, assuming approximately 15% drop out.

Statistical Analysis:

Patient Characteristics:

Standard baseline characteristics of gender, age, and race will be summarized for all patients. Treatment group comparisons will be made using Fisher's exact test for categorical data and an analysis of variance (ANOVA), with an independent factor for treatment for continuous data. Diagnosis, illness characteristics, and baseline efficacy and safety measures will be analyzed in a similar manner.

Efficacy:

The primary objective of this study is to assess the effect on neuropathological progression of 2 different LY3202626 doses in patients with mild AD dementia compared with placebo, measured by change in ¹⁸F-AV-1451 PET standardized uptake value ratio (SUVr) at baseline and week 52. The primary measurement is change from

baseline ¹⁸F-AV-1451 PET SUVr at Week 52. An analysis of covariance (ANCOVA) will be used to statistically evaluate change in ¹⁸F-AV-1451 PET from baseline at 52 weeks post-dose.

Statistical analyses of mean change in efficacy and health outcome measures will be conducted. Generally, statistical assessment of the efficacy and health outcome measures will be a mixed model repeated measure (MMRM) or an ANCOVA. The primary comparison will be between LY3202626 12 mg versus placebo at endpoint.

Safety:

Safety will be assessed by summarizing and analyzing adverse events (AEs), laboratory analytes, vital signs, electrocardiograms (ECGs), skin examinations, and eye examinations during the treatment period. For continuous safety measurements, a change from baseline will be analyzed using MMRM or ANCOVA model. Safety analyses for the treatment period will include comparisons between LY3202626 dose groups and placebo. All hypotheses will be tested at a 2-sided 0.05 significance level. No adjustments for multiple comparisons will be made.

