5.1. Overall Design

Study LLCF is a multicenter, randomized, double-blind, placebo-controlled study in patients with mild AD dementia. This study (Study LLCF) will enroll patients with mild AD dementia using National Institute on Aging-Alzheimer's Association (NIA-AA) work group consensus guidelines (McKhann et al. 2011) with amyloid deposition confirmed by florbetapir F 18 PET imaging. The treatment phase will be 52 weeks.

Figure LLCF.1 illustrates the study design.

Abbreviations: AD = Alzheimer's disease; FP = follow-up period; LY = LY3202626.

Note: This is a multicenter, randomized, parallel-group, 52-week-long double-blind, placebo-controlled, study of 2 fixed dose levels of LY3202626 (3 mg and 12 mg) in patients with mild AD dementia and evidence of amyloid pathology.

Approximately 380 mild AD dementia patients will be enrolled (approximately 167 in the placebo and 12 mg groups, and approximately 45 in the 3 mg group).

Figure LLCF.1. Illustration of study design for Clinical Protocol I7X-MC-LLCF.

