7.2. Method of Treatment Assignment

Patients who meet all criteria for enrollment will be randomized to double-blind treatment at Visit 3. Assignment to treatment groups will be determined by a computer-generated random sequence using an interactive web-response system (IWRS). Randomization will be stratified by the following two factors: 1) patient participation of LP addendum (Y/N) and 2) type of perfusion (dynamic /static) of PET imaging center. The IWRS will be used to assign bottles containing double-blind investigational product to each patient. Sufficient study drug will be dispensed to supply the patient until the next visit. Site personnel will confirm that they have located the correct drug by entering a confirmation number found on the container into the IWRS.

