10.3.3. Efficacy Analyses

10.3.3.1. Primary Analyses

The primary objective of this study is to assess the PD effect of 2 different LY3202626 doses (3 mg and 12 mg) in patients with mild AD dementia compared with placebo, measured by change in ¹⁸F-AV-1451 PET SUVr at baseline and Week 52. The primary measurement is change from baseline ¹⁸F-AV-1451 SUVr. The method for calculating the SUVr will be provided in the SAP. ANCOVA will be used to statistically evaluate change in SUVr from baseline at 52 weeks post-dose. The ANCOVA will include the fixed, categorical effects of treatment dose, and the continuous, fixed covariate of baseline ¹⁸F-AV-1451 SUVr.

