## 5. A Priori Statistical Methods

### 5.1. General Considerations

All tests of treatment effects of biological efficacy or clinical efficacy will be conducted at a 1-sided  $\alpha=.10$ , unless otherwise stated. Safety assessments will be conducted at a 2-sided  $\alpha=.05$ .

A repeated measures analysis refers to a restricted maximum likelihood (REML)-based, mixed effects repeated measures analysis using all the longitudinal observations at each post-baseline visit.

All analyses will follow the intent-to-treat (ITT) principle unless otherwise specified. An ITT analysis is an analysis of data by the groups to which subjects are assigned by random allocation, even if the subject does not take the assigned treatment, does not receive the correct treatment, or otherwise does not follow the protocol.

When change from baseline is assessed, subjects will be included in the analysis only if both a baseline and a postbaseline measure are available. Unless otherwise defined, Visit 3 is the baseline visit, and baseline value is defined as last value available before or at Visit 3.

All total and subscale scores will be derived from individual items. If any individual item is missing, the corresponding total and subscale scores will be considered missing, except for the ADAS-Cog13 and ADCS-iADL, which will be imputed.

A repeated measures analysis model will include the fixed, categorical effects of treatment, visit, and treatment-by-visit interaction, as well as the continuous, fixed covariates of baseline, baseline-by-visit interaction, and age at baseline.

When an analysis of covariance (ANCOVA) model is used to analyze a continuous efficacy variable, the model will contain the main effects of treatment with baseline value and age at baseline added as covariates. For ANCOVA analysis on change from baseline to Week 52 endpoint, change from baseline to last observation during treatment period will be used if patients do not have Week 52 observation available.

Categorical comparisons between treatment groups will be performed using Fisher's exact tests or logistic regression where appropriate.

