### 5.2. Adjustments for Covariates

The repeated measures models will include the fixed, categorical effects of treatment, visit (categorical covariate), treatment-by-visit interaction, as well as the continuous, fixed covariate of baseline, baseline-by-visit interaction, and age at baseline.

When an ANCOVA model is used to analyze a continuous efficacy or safety variable, the model will contain the main effects of treatment and appropriate baseline value and age at baseline included as covariates.

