## **5.11. Efficacy Analyses**

### **5.11.1. Primary Outcome and Methodology**

The primary objective of this study is to assess the PD effect of 2 different LY3202626 doses (3 mg and 12 mg) in patients with mild AD dementia compared with placebo, measured by change from baseline in 18F-AV-1451 PET SUVrs at Week 52.

The primary statistical analysis is the ANCOVA, which will be used to statistically evaluate change in composite SUVr from baseline at 52 weeks post-dose. The ANCOVA will include the fixed, categorical effects of treatment dose, and the continuous, fixed covariate of baseline Tau PET SUVr and age at baseline.

Change from baseline analyses will be conducted on SUVrs computed from the following 3 composite regions with the bimodal white matter serving as the reference region: MUBADA (primary), Delta\_Z, and the frontal lobe region defined as a weighted average (weights being the number of voxels in the region) of SUV counts, averaged bilaterally, in the following Region of Interests (ROIs):

- cingulum anterior
- Inferior frontal gyrus, opercular part
- Inferior frontal gyrus, orbital part
- Inferior frontal gyrus, triangular part
- Middle frontal gyrus
- Middle frontal gyrus, orbital part
- Superior frontal gyrus
- Superior frontal gyrus, medial
- Superior frontal gyrus, orbital part

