### **5.11.2. Key Secondary and Exploratory Outcomes**

The additional clinical and outcome measurements listed below will be analyzed separately using a mixed-effect model for repeated measures (MMRM) analysis.

The change from baseline score at each scheduled post-baseline visit (according to the Study Schedule - data collected at unscheduled visits, including early discontinuation visits if not matching the study schedule, will not be included in this analysis) during the treatment period will be the dependent variable. The model will include the fixed effects of treatment, visit

(categorical covariate), treatment-by-visit interaction, baseline age, baseline score (continuous covariate) and baseline-by-visit interaction. Visit will be considered a categorical variable with values equal to the visit numbers at which the scales were assessed. An unstructured covariance matrix will be used to model the within-subject variance-covariance errors. If the unstructured covariance structure matrix results in a lack of convergence, the following tests will be used in sequence: heterogeneous Toeplitz covariance structure, heterogeneous autoregressive covariance structure, heterogeneous compound symmetry covariance structure, and compound symmetry covariance structure. The Kenward-Roger approximation will be used to estimate the denominator degrees of freedom. Significance tests will be based on LSMeans using a 1-sided Alpha of 0.10. Analyses will be implemented using SAS PROC MIXED. Longitudinal graphs of the LSMeans estimates at each visit from the model will be plotted and the LSMeans and 95% confidence intervals (CIs) results will be summarized in a summary table.

The secondary outcomes that will be analyzed are the following:

- Change from baseline in ADAS-Cog13.
- Change from baseline in ADCS-iADL.
- Change from baseline in iADRS.

The exploratory outcomes that will be analyzed are the following:

- Change from baseline in MoCA total scores.
- Change from baseline in FAQ.
- Change from baseline in MMSE total scores.
- Change from baseline in ECog.

The following exploratory outcomes will be analyzed using the ANCOVA model described in Section 5.1:

- Change from baseline in NPI total scores.
- Change from baseline in BASQID total scores.

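### Randomisation is stratified by PET-centre perfusion type, but no efficacy or imaging model includes it: the 12 mg tests may be slightly conservative, and the 3 mg contrast is exposed if the dynamic/static mix shifts between allocation phases

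*Protocol*

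**What the plan says.** Protocol 7.2: "Randomization will be stratified by the following two factors: 1) patient participation of LP addendum (Y/N) and 2) type of perfusion (dynamic /static"). The second factor describes the PET imaging centre.

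Allocation runs in two phases. It starts at 1:1:1; once about 45 patients are in each arm, "randomization will change to 1:1 with subjects entering either the 12 mg or placebo arm" (Protocol Synopsis, Treatment Arms and Duration). The planned arms are "approximately 167 in the placebo and 12 mg groups, and approximately 45 in the 3 mg group" (Protocol 5.1).

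The models are:

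- **Primary tau PET ANCOVA.** Protocol 10.3.3.1: "The ANCOVA will include the fixed, categorical effects of treatment dose, and the continuous, fixed covariate of baseline" SUVr. SAP 5.11.1 adds age: "continuous, fixed covariate of baseline Tau PET SUVr and age at baseline".
- **General ANCOVA.** SAP 5.1: "the model will contain the main effects of treatment with baseline value and age at baseline added as covariates". SAP 5.2 has the same terms and applies them widely: "When an ANCOVA model is used to analyze a continuous efficacy or safety variable".
- **Clinical MMRM (SAP 5.11.2).** Treatment, visit, "treatment-by-visit interaction, baseline age, baseline score (continuous covariate) and baseline-by-visit interaction".
- **Subgroup model (SAP 5.11.3).** Baseline, treatment, subgroup and the interaction.
- **Plasma A-beta MMRM (SAP 5.12.1).** Log baseline, treatment, visit and treatment-by-visit.
- **AV-45, perfusion PET, vMRI and annualised change (SAP 5.12.3 to 5.12.5).** Baseline, age and treatment.

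None of these contains perfusion type, LP participation or a term for allocation phase. No restriction to concurrently randomised placebo is stated. SAP 5.12.2 reports that very few patients joined the LP addendum.

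**The concern.** Stratified randomisation balances the arms on the chosen factors. A model that leaves those factors out keeps their variance in the residual, so its standard errors do not reflect the balance that the design produced. If the factor predicts outcome, tests between arms balanced on it become conservative.

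The change of allocation ratio adds a second problem. Stratified blocks balance the arms within each phase, not an early-phase arm against placebo pooled over both phases. If the share of patients from dynamic centres differs between phases, 3 mg and placebo differ on perfusion type, and the unadjusted contrast can be biased in either direction. That contrast is part of the primary objective (SAP 4.1).

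The link is most plausible for exploratory perfusion SUVr, where the name suggests that perfusion type is how the endpoint is acquired. For tau PET, vMRI and cognition the documents show no direct link.

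**Working it through.** **The plan's own numbers.** 320 / 0.85 = 376.5, so 377 against the stated 380 (Protocol 5.2), and 380 x 0.85 = 323. The arms sum to 167 + 167 + 45 = 379. These agree. The stated power (at least 79% at 30% drop-out, Protocol 10.1.1) cannot be checked, because the effect size and SD are not visible.

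**Inputs from the documents.** One-sided alpha 0.10 (SAP 5.1), so z = 1.2816; arm sizes and 15% drop-out as above. **Assumed inputs.** R2, the share of residual variance (after the model's existing covariates) explained by perfusion type; an equal dynamic/static split; and the drift in dynamic share between phases.

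**What R2 is plausible?** With an equal split and a difference in change of d residual SDs between types, R2 = (d^2/4)/(1 + d^2/4). So R2 of 1%, 5% and 10% need d = 0.20, 0.46 and 0.67. Suppose instead the types differ only in level, by 1 SD, and the scan-to-scan correlation is r. Then R2 = 1 - [2(1-r) - (1-r)^2] / [2(1-r) - (1-r)^2/1.25]. This gives 1.0%, 2.2% and 3.4% for r = 0.9, 0.8 and 0.7.

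**12 mg versus placebo.** SE ratio = 1/sqrt(1 - R2); size = 1 - Phi(1.2816/sqrt(1 - R2)). Neither depends on n.

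| R2 | SE overstated by | Actual size |
|---|---|---|
| 0% | 0% | 10.0% |
| 1% | 0.5% | 9.9% |
| 3.4% | 1.7% | 9.6% |
| 5% | 2.6% | 9.4% |
| 10% | 5.4% | 8.8% |

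**3 mg versus placebo.** Placebo patients in the later phase: 167 - 45 = 122. Imbalance in dynamic share = (122/167) x drift = 0.731 x drift. Bias = d x 0.731 x drift. With 15% drop-out, 45 x 0.85 = 38.25 and 167 x 0.85 = 141.95, so SE = sqrt(1/38.25 + 1/141.95) = 0.182 SD. Size = 1 - Phi(1.2816 x sqrt(1 + d^2/4) -/+ bias/SE).

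| R2 | Drift | Bias (SD) | Size if bias favours drug | Size if not |
|---|---|---|---|---|
| 1% | 10 points | 0.015 | 11.4% | 8.6% |
| 1% | 20 points | 0.029 | 13.0% | 7.4% |
| 5% | 10 points | 0.034 | 12.9% | 6.7% |
| 5% | 20 points | 0.067 | 17.2% | 4.6% |

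For example, at R2 5% and 20 points: bias = 0.459 x 0.731 x 0.20 = 0.067; bias/SE = 0.368; 1.2816 x sqrt(1.0526) = 1.315; 1 - Phi(1.315 - 0.368) = 17.2%. With no drift there is no bias, and the test is conservative as for 12 mg.

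**Early termination.** The SAP's revision history says most patients will lack a Week 52 observation. If the later phase supplies an assumed 50% of placebo scans (38 versus 76 scans), the four inflated sizes fall to 10.8%, 11.8%, 11.5% and 13.9%.

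**LP participation.** At an assumed 3% to 5% participation and a 0.5 SD difference, the SE is overstated by 0.4% to 0.6%.

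**Simulation check.** 40,000 trials per setting: 135 patients 1:1:1, then 244 at 1:1, permuted blocks within type, 15% random drop-out, Monte Carlo SE about 0.15 points.

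| Contrast | R2 | Drift | Size without the factor | Size with it |
|---|---|---|---|---|
| 12 mg | 1% | none | 9.8% | 9.9% |
| 12 mg | 5% | none | 9.6% | 10.0% |
| 3 mg | 1% | 10 points | 11.2% | 9.9% |
| 3 mg | 1% | 20 points | 13.0% | 10.1% |
| 3 mg | 5% | 10 points | 13.1% | 10.1% |
| 3 mg | 5% | 20 points | 17.8% | 10.3% |

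**The case against.** The strongest reply has three parts.

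First, the effect on 12 mg versus placebo, the named main comparison for secondary and exploratory outcomes, is trivial: no bias, and at R2 1% a difference within simulation error. That stands, and it is why the point is minor.

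Second, the 3 mg bias arises from comparing an early-phase arm with placebo from both phases. Any prognostic factor that drifts would cause it, including shorter follow-up in later enrollees after early termination. That also stands. Adjusting for perfusion type closes one route only; other phase differences would need a phase term or a concurrent-placebo sensitivity analysis. The simulated return to about 10% reflects a setting where nothing else drifts.

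Third, the larger figures stack assumptions. A size of 17.2% needs a 20-point drift, a 0.46 SD difference in change and a favourable direction, and R2 5% exceeds what a 1-SD level difference yields. Dynamic and static are not defined, so the link to perfusion SUVr is inferred. Protocol 3.2 puts the primary focus for 3 mg on safety. All of this limits the size, but none of it gives a reason for leaving the factor out.

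Two further objections do not stand. The existing covariates do not answer the point, because R2 here is the variance left after them. Nor does the cognitive or plasma model need a mechanism: the case for adjustment there is that the trial randomised by this factor.

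**Conclusion.** The concern holds, at minor severity. Both stratification factors are absent from every efficacy and imaging model, without explanation.

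For 12 mg versus placebo the inference is valid and at most slightly conservative. For 3 mg versus placebo the direction of error is not guaranteed: about 73% of any drift in the dynamic/static mix would carry into the contrast at the planned numbers, and less if early termination removes later placebo scans.

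Every size quoted depends on an assumed R2, stratum split and drift. If perfusion type does not predict change, the omission does no harm and adjustment loses essentially nothing. Omitting LP participation is negligible.

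**What to change.** Add perfusion type (dynamic/static) as a fixed categorical effect to:

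- the ANCOVAs in SAP 5.1, 5.2 (efficacy variables only), 5.11.1, 5.11.3 and 5.12.3 to 5.12.5, including annualised change;
- the MMRMs in SAP 5.11.2 and 5.12.1.

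Add LP participation only if blinded stratum counts, taken before database lock, show that its effect can be estimated. Safety ANCOVAs can stay as they are. If either factor is left out, state why.

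The cost is a one-line rule in the SAP, carried into the listed sections, and one or two degrees of freedom. Both factors are fixed before randomisation and already held in the IWRS, so no new data are needed.

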7.2.1. Selection and Timing of Doses

The doses will be administered at approximately the same time on each day, preferably in the morning. For patients who desire to regularly dose at another time of day, exceptions can be made in consultation with the Lilly medical monitor. The first dose should be taken the morning after the first dispensing of drug at Visit 3. Patients will be requested to record the actual date and time of the 2 dose administrations prior to each visit at which PK will be collected (for example, the date and time of the previous day's dose, as well as the date and time of the dose prior to that). If a dose is administered at the clinic, that date and time should also be recorded. The date and time of these dose administrations will be recorded in the patient's eCRF. If the patient fails to follow the dosing instructions for those visits where a dose is to be administered at the site, blood samples are still to be collected according to the Schedule of Activities (Section 2) and as described above. On those visits where the dose is to be administered at the site, if the patient fails to follow this instruction and is dosed prior to sample collection, an additional dose will not be administered at the visit.

7.3. Blinding

This is a double-blind study.

To preserve the blinding of the study, a minimum number of Lilly personnel will see the randomization table and treatment assignments before the study is complete.

Emergency unblinding for AEs may be performed through the IWRS, which may supplement or take the place of emergency codes generated by a computer drug-labeling system. This option may be used ONLY if the patient's well-being requires knowledge of the patient's treatment assignment. All calls resulting in an unblinding event will be recorded and reported by the IWRS.

If an investigator, site personnel performing assessments, patient, or study partner is unblinded, the patient must be discontinued from the study. In cases where there are ethical reasons to have the patient remain in the study, the investigator must obtain specific approval from a Lilly-designated medical monitor for the patient to continue in the study.

In case of an emergency, the investigator has the sole responsibility for determining if unblinding of a patient's treatment assignment is warranted. Patient safety must always be the first consideration in making such a determination. If the investigator decides that unblinding is warranted, the investigator should make every effort to contact the Lilly-designated medical monitor prior to unblinding a patient's treatment assignment unless this could delay emergency treatment of the patient. If a patient's treatment assignment is unblinded, Lilly must be notified immediately.

7.4. Dosage Modification

Dose adjustments are not allowed in this study.

7.5. Preparation/Handling/Storage/Accountability

Clinical trial material will be stored in a secure, locked location maintained at the conditions specified on the label. A record of inventory transactions will be maintained that will allow accountability of all study drug. Handling and storage instructions for patients will be included on labeling of clinical trial materials.

7.6. Treatment Compliance

The administration of all study medication should be recorded in the appropriate sections of the eCRF

Compliance will be assessed at in-clinic visits via capsule counts when the study medication packaging and any unused study medication are returned at study visits. The patient should be instructed to bring all unused medication to the clinic at each visit so that the clinic staff can record the amount of medication used since the last visit.

Only patients who consume at least 80% of the prescribed daily dose (based on capsule count) during this study will be considered compliant. Similarly, patients will be considered significantly noncompliant if they are judged by the investigator to have intentionally or repeatedly taken more than the prescribed amount of medication. Patients regarded as noncompliant may be discontinued at the investigator's discretion, in consultation with the Lilly-designated medical monitor.

Drug accountability will be emphasized at the start-up meeting, and drug accountability will be monitored throughout the study.

